## 7.2 Randomization

After registration, research staff will randomize patients via MSK's secure Clinical Research Database (CRDB) using permuted blocks of random length. The allocation ratio will be 1:1 for ACU:OPI. Using the institutional randomization standard procedure with random blocks for RCTs will ensure full allocation concealment. Randomization will be stratified by study site, primary cancer diagnosis (MM versus HD versus NHL) and transplantation setting (inpatient versus outpatient) to ensure these characteristics are comparably distributed between the two study arms.

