## 9.0 PRE-TREATMENT/INTERVENTION

Enrolled patients will receive the following baseline assessments within 4 weeks before the first dose of HiChemo. Detailed descriptions of each assessment are in Section 11.0 and 13.1.

- Demographic and Clinical Features
- Symptom Burden (MDASI-BMT), paper or electronic
- Brief Pain Inventory – Short Form (BPI), paper or electronic
- Patient-Reported Oral Mucositis Symptom Scale (PROMS) ,paper or electronic
- Pain Medication Side Effects Questionnaire,paper or electronic
- Quality of Life (PROMIS-29), paper or electronic
- Adverse Events (CTCAE v5)
- Opioid Risk Tool (ORT), paper or electronic
- Acupuncture Expectancy Scale (AES), paper or electronic

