## 11.0 EVALUATION DURING TREATMENT/INTERVENTION

We will assess all study participants for the study outcomes at baseline (within 4 weeks before HiChemo) and on or about days 7, 15, 30, and 90 after the first dose of HiChemo (See Schema in Section 4.0). The total burden in time to patients is about 30-45 minutes at each time point.

The following outcome measurements will be carried out on and about Day 7, 15, 30 and 90 (Day 0 being the day of first dose of HiChemo), either in the Integrative Medicine or BMT clinic in order to minimize unnecessary visits. The instruments are attached in appendices, and may be administered electronically (on a tablet if in clinic, via secure link if at home) or on paper.

- Opioid Use (drug administration record while inpatient and pill count while outpatient)
- Symptom Burden (MDASI-BMT)
- Brief Pain Inventory – Short Form (BPI)

- Patient-Reported Oral Mucositis Symptom Scale (PROMS)
- Pain Medication Side Effects Questionnaire
- Quality of Life (PROMIS-29)
- Adverse Events (CTCAE v5)

Collection of demographic and clinical features (diagnosis, disease status, chemotherapy regimen and mortality) data and assessment of use of healthcare resources will also be carried out on and about Day 90. Use of healthcare resources includes the length of hospital stays and transfers to the intensive care unit during HSCT, and total inpatient days, emergency room visits and readmissions during the first 30 days post-HSCT.

Schema of Data Collection	By Patient vs. By Study Team (ST)	Baseline	Day 7 (± 2 day)	Day 15 (± 3 days)	Day 30 (± 7 days)	Day 90 (± 14 days)
Demographic and Clinical Features	ST	X				X
Opioid Use (Primary Outcome)	Patient and ST	X	X	X	X	X
Symptom Burden (MDASI-BMT)	Patient	X	X	X	X	X
Brief Pain Inventory – Short Form (BPI)	Patient	X	X	X	X	X
Patient-Reported Oral Mucositis Symptom Scale (PROMS)	Patient	X	X	X	X	X
Pain Medication Side Effects Questionnaire	Patient	X	X	X	X	X
Quality of Life (PROMIS-29)	Patient	X	X	X	X	X
Adverse Events (CTCAE v5)	ST	X	X	X	X	X
Opioid Risk Tool (ORT)	Patient	X				
Acupuncture Expectancy Scale (AES)	Patient (ACU)	X				
Use of Health Care Resources	ST					X

\*Day 0 = Day of the first dose of high dose chemotherapy

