to screen for opioid misuse risk, and takes 2 minutes to complete. This data will be collected at baseline and used in Heterogeneity of Treatment Effect (HTE) analysis to assess whether it influences the effects of acupuncture. Expectancy for acupuncture may influence its clinical effects. We will assess patients at baseline using the Acupuncture Expectancy Scale (AES). This is a validated instrument (takes about 3 minutes to complete) with an internal consistency (Cronbach's  $\alpha$ ) of 0.95 and test-retest reliability of 0.62 over four weeks without acupuncture treatment. This data will be used as a variable in HTE analyses for predictor to response and sensitivity analyses. We will also track use of healthcare resources, such as the length of hospital stays and transfers to the intensive care unit during HSCT, and emergency room visits and readmission during the first 30 days post-HSCT. These are exploratory endpoints to generate preliminary data about impact on the health care system, e.g. iatrogenic adverse events from opioids and delayed discharge from opioid side effects.

All patient-reported measures will be administered either electronically (on a tablet if in clinic, via secure link if at home) or on paper.

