**14.2.5. Exploratory Aim 2, Heterogeneity of Treatment Effect (HTE).** We expect patients will respond differently to study interventions but we do not have enough preliminary data to generate hypotheses. Our HTE analyses will be exploratory and hypothesis-generating. We will explore whether sex, race, ethnicity, gender, primary cancer diagnosis (MM versus HD versus NHL), Opioid Risk Tool (ORT), Acupuncture Expectancy Scale (AES) score, or concurrent use of other medications with analgesic effects influence response to interventions in this population. We will add these variables and variable-by-arm interaction terms to our Day 7 and Day 90 logistic and linear regression models to identify potential patient-level factors associated with differential responses to treatment with respect to our primary and secondary outcomes. Each variable of interest will be assessed for HTE in a separate model. We will guard against inflated type I errors due to multiple testing by adjusting the variable-by-intervention interaction p-values for the false discovery rate. We intend to approach the evaluation of HTE based on existing literature and patient/clinician input. Our current focus on evaluating and reporting HTE will be based on the approach proposed by Kent et al. However we will also apply promising emerging Bayesian and machine learning methods, which can identify HTE and subgroups based on multiple variables simultaneously and are potentially more powerful than traditional univariate methods. We recognize that these types of sub-group analyses, although patient-centered, may need to be interpreted with caution and cannot replace the primary analyses.

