**14.3. Missing Data.** We will first explore whether missingness is associated with observed variables (particularly randomization arm and the baseline outcome measures) by comparing patients with complete and incomplete data. Of note, our general longitudinal data analysis approaches described above (GLMM and LMM) validly include patients with incomplete data under the missing at random assumption. However, our exploration of the data may deem the missing at random assumption to be inappropriate, and not all our hypotheses will be tested using these longitudinal modeling approaches. In these cases, we will use well-established methods such as multiple imputation and pattern mixture models to help us deal with these issues. We will perform sensitivity analyses to evaluate the robustness of our main findings by using multiple imputation to impute the missing outcomes (particularly for Day 7 and Day 90) and duplicating the analyses using the multiply imputed data sets.

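### The Section 11.0 schedule limits the Acupuncture Expectancy Scale to ACU patients, while Sections 9.0 and 13.1 do not; if the schedule is followed, the AES-by-arm interaction in Section 14.2.5 cannot be estimated

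*Combined protocol and SAP*

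**What the plan says.** Four places in the combined protocol and SAP bear on who completes the Acupuncture Expectancy Scale (AES) and what it is for.

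- **Section 9.0** opens its list of baseline forms with "Enrolled patients will receive the following baseline assessments within 4 weeks before the first dose of HiChemo" and includes "Acupuncture Expectancy Scale (AES), paper or electronic". No arm is mentioned.
- **Section 13.1** says "We will assess patients at baseline using the Acupuncture Expectancy Scale (AES", again for patients generally. On use, it says "This data will be used as a variable in HTE analyses for predictor to response and sensitivity analyses".
- **Section 11.0** has a data collection table with a respondent column headed "By Patient vs. By Study Team (ST". For the AES, that column gives the patient with ACU in brackets. The Opioid Risk Tool, the other baseline-only questionnaire used as a moderator, is assigned to the patient with no arm label.
- **Section 14.2.5** names the AES score among eight candidate moderators and gives the model: "We will add these variables and variable-by-arm interaction terms to our Day 7 and Day 90 logistic and linear regression models". Each moderator gets its own model, and the section calls these analyses exploratory.

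Two further sections matter for the consequences. Section 7.2 says "After registration, research staff will randomize patients via" the central database. Section 14.3 describes sensitivity analyses "using multiple imputation to impute the missing outcomes".

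**The concern.** ACU is the protocol's defined label for the acupuncture arm, so the natural reading of the table entry is that OPI patients do not complete the form. That conflicts with Section 9.0 and with the analysis in Section 14.2.5. Nothing in the documents resolves the difference.

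To ask whether expectancy modifies the effect of ACU versus OPI, one must compare the AES–outcome relation between the arms. With scores from one arm only, there is nothing to compare. A slope within ACU could mean that expectancy changes the benefit of acupuncture, or that hopeful patients do better whatever they receive.

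The control here is usual care rather than sham, and Section 13.1 itself says that expectancy may influence acupuncture's clinical effects, so this is a relevant moderator. It is also a baseline measure: if it is not taken on time, no later amendment recovers it.

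**Working it through.** **Inputs.** 300 patients randomised, 150 per arm, and 135 per arm evaluable after 10% attrition (Section 14.1). The model form is from Section 14.2.5. The plan states no figure for this analysis, so there is none to reproduce.

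**1. The table.** It has 11 rows. Only the AES row names an arm.

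**2. Estimability.** Write the linear predictor, for the logistic or the linear model, as

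η = b0 + b1·arm + b2·AES + b3·(arm × AES), with arm = 1 for ACU and 0 for OPI.

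- *AES in ACU only.* Every usable row has arm = 1, so η = (b0 + b1) + (b2 + b3)·AES. The arm column equals the intercept column and the product column equals the AES column. Rank is 2 of 4. Only the sums b0 + b1 and b2 + b3 can be estimated; b3 alone cannot. Up to 150 of 300 patients have a score.
- *AES in ACU, OPI filled with a constant c.* OPI rows are (1, 0, c, 0) and ACU rows are (1, 1, AES, AES). Rank is 3 of 4, and b2 and b3 still cannot be separated.
- *AES in both arms.* Rank is 4 of 4, and b3 is estimable.

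A numerical check at 150 per arm gave ranks 2, 3 and 4 for these three cases. The result does not depend on the AES values, provided they vary between patients.

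**3. What the remaining slope means.** The within-ACU slope is b2 + b3, prognostic part plus modifying part. As an illustration, assume a total of −0.30 SD of outcome per SD of AES:

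| Truth | Within-ACU slope | Two-arm interaction (b3) |
|---|---|---|
| wholly prognostic (b2 = −0.30, b3 = 0) | −0.30 | 0.00 |
| wholly modifying (b2 = 0, b3 = −0.30) | −0.30 | −0.30 |

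A simulation of 2,000 trials with 135 per arm, AES and residuals standard normal (assumed), gave mean within-ACU slopes of −0.303 and −0.300, and mean two-arm interactions of −0.003 and −0.302. Data from ACU alone cannot distinguish the two cases.

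**4. Imputation.** Section 14.3 describes imputing outcomes. It does not provide for a covariate absent from a whole arm. Imputing AES in OPI would make the AES–outcome relation there an assumption, so the interaction would be assumed too.

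**5. Precision if both arms are collected.** For a continuous outcome with unit residual SD and unit-SD AES (assumed), each arm's slope has variance of about 1/n. Hence SE(b3) = √(2/135) = 0.122. The slope difference detectable with 80% power at two-sided 0.05 is (1.960 + 0.842) × 0.122 = 0.34 SD per SD of AES; with 150 per arm it is 2.802 × √(2/150) = 0.32. This is before the false discovery rate adjustment and does not apply to the binary opioid endpoints. It is a different quantity from the 0.34 SD mean difference in Section 14.2.3; the numbers agree because the variance expression is the same. The finding does not depend on this step.

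**6. Timing.** A form meant for ACU patients only can be given only once allocation is known. Section 7.2 places randomisation after registration and Section 9.0 sets a 4-week window for baseline forms. Neither fixes the order of the two, so expectancy could be recorded after the patient knows the arm.

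**The case against.** The strongest case on the other side is about weight.

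- **Everything affected is exploratory.** The plan says so, and separate models mean that losing the AES leaves the other seven moderators intact. This stands, and it limits the importance of the point.
- **The harm is conditional.** Sections 9.0, 13.1 and 14.2.5 all fit or require collection in both arms, so the table entry may be a slip. That is plausible. But the schedule is a natural working guide for site staff, and the two sites could follow different sections.
- **Section 13.1 is not strictly opposed to the table.** An unqualified reference to patients is less specific than the table, and using the AES to predict response could describe an analysis within ACU. This has some force: the firmer conflicts are with Section 9.0 and Section 14.2.5. But Section 13.1 places that use within the heterogeneity analyses, which Section 14.2.5 defines by interactions with arm. If a within-ACU analysis is meant, Section 14.2.5 is wrong for the AES and still needs changing.
- **Completing the form before allocation is disclosed is good practice rather than a correction.** Agreed; no text forbids it or requires it, and it adds nothing to the severity.

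**Conclusion.** The concern holds. The current text gives two incompatible rules for who completes the AES. Under the schedule's rule, the planned AES-by-arm analysis cannot be run at Day 7 or Day 90, because the model has rank 2 of 4. Under the other rule it can be run, and the table entry is the only error.

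The conclusion rests on reading the bracketed ACU as a restriction to that arm. The rank result needs no assumption about effect size; the −0.30 slopes and the precision figures are illustrations only.

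The reach is narrow: one of eight moderators in Exploratory Aim 2, and any AES sensitivity analysis that compares arms (Section 13.1 does not say whether these do). The primary and secondary comparisons, type I error control and sample size are unaffected. It should still be corrected, because the data loss would be permanent and the correction is small.

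**What to change.** Reconcile the sections in one of two ways.

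1. **Preferred: collect the AES in both arms.** Delete the arm restriction from the AES row of the Section 11.0 table so that it matches Sections 9.0 and 13.1. Section 14.2.5 then stands as written. As an added recommendation, state that the form is completed after consent and before allocation is disclosed. The cost is one table entry and, by Section 13.1's estimate, about 3 minutes per OPI patient. The small drawback is that OPI patients answer questions about a treatment they will not receive.
2. **If ACU-only collection is intended:** state this in Sections 9.0 and 13.1, replace the AES interaction in Section 14.2.5 with a within-ACU predictor analysis, and say that this analysis cannot show effect modification. Exploratory Aim 2 in Section 2.0 should be aligned. The cost is a few sentences, and the AES question is given up as a question about heterogeneity of treatment effect.

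If enrolment has begun, establish which rule each site has applied and how many OPI patients have a baseline score.

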### **13.2 Criteria for Study Endpoint Evaluability**

All patients who are randomized and who have their opioid use evaluated at Day 7 will be considered evaluable for the Day 7 opioid primary endpoint. Similarly, patients who have their opioid use evaluated at Day 90 will be evaluable for the Day 90 opioid primary endpoint. For the Day 7 symptom burden primary endpoint, all patients who are randomized and who have at least a baseline MDASI-BMT Total Symptom Severity score will be considered evaluable. In general, patients will be considered evaluable for continuous study endpoints as long as they have at least the baseline measurement. No patient will be replaced after randomization. All randomized patients meeting these additional evaluability criteria will be included in the analyses using the modified intention-to-treat (ITT) principle (i.e. participants will be analyzed according to the treatment group to which they will be randomly allocated regardless of treatment adherence status).

## **14.0 BIOSTATISTICS**

This is a multicenter, two-arm randomized controlled trial to compare the effects of two pain management strategies on opioid use, symptom burden, and other patient-reported outcomes among patients receiving high-dose chemotherapy (HiChemo) followed by HSCT. Opioid-naïve adult multiple myeloma, Hodgkin disease, and non-Hodgkin lymphoma patients undergoing HiChemo followed by HSCT will be randomized (at 1:1 ratio, see Section 7.2) to receive either acupuncture as a first-line pain preventive measure during HiChemo with opioids as back-up pain treatment (ACU), or opioids as first-line pain treatment (OPI). Study outcomes will be measured at pre-HiChemo baseline and at Days 7, 15, 30, and 90 after the first dose of HiChemo, with the Day 7 (short-term) and Day 90 (long-term) outcomes of particular interest. We expect to accrue approximately 12 patients per month, and we anticipate the study will be open to enrollment for approximately 30 months. We expect the

total study duration to be 3 years.

**14.1. Sample Size Considerations.** This study has 3 primary endpoints: opioid use at Day 7, opioid use at Day 90, and symptom burden at Day 7. The statistical plan takes that into consideration. Our overall Type I error rate for testing these 3 primary endpoints is set to alpha = 0.05. To maintain this Type I error rate, we will allocate alpha = 0.02 to each of the tests of opioid use at Day 7 and at Day 90, and we will allocate alpha = 0.01 to the test of symptom burden at Day 7.

In our pilot study, among “opioid-naïve” patients, 25% of sham acupuncture (SA) patients and 7% of true acupuncture (TA) patients were opioid users at Day 90. For our sample size/power estimates for Aim 1, we conservatively assume that patients in the OPI arm will have similar Day 90 opioid usage (25%) as the SA patients in our prior study, and that 10% of patients in the ACU arm will be using opioids at Day 90 (slightly higher than the TA arm in our pilot study). This translates to a relative reduction of 60% fewer opioid users in the ACU arm, and an odds ratio of 0.33, which would be considered clinically meaningful. The attrition rate was only 5% in our pilot study. However, we will conservatively plan for a high 10% attrition rate by randomizing 300 patients (150 per arm) in order to obtain 270 patients (135 per arm) with evaluable Day 90 endpoints. With an initial sample size of 300 patients and a 10% attrition rate, we will have 81% statistical power to detect this Day 90 difference between the two arms (i.e. 10% vs 25%) at a significance threshold of  $p<0.02$  using logistic regression analysis and a two-sided significance test. It is possible that the OPI group will have higher opioid use than the SA patients in our pilot study, as sham acupuncture is known to have some placebo effect. We therefore expect a larger effect size than we observed in the pilot study where true acupuncture was compared to sham acupuncture. In that scenario, assuming 30% in the OPI group use opioids versus 10% in ACU group, our power will increase to 96%.

We based our sample size exclusively on having adequate power for the Day 90 comparison of opioid use. This was due to the high public health priority to find pain interventions that can reduce long-term opioid use. That said, we expect the Day 7 comparison to have similar power as the Day 90 comparison. We believe this is a conservative assumption, and that we most likely have higher power at Day 7 due to lower attrition and potentially a larger effect size at Day 7 relative to Day 90. For example, in our pilot study, 20% of sham acupuncture (SA) patients were using opioids at Day 5 (opioid usage not collected at Day 7) compared to none of the true acupuncture (TA) patients.

For our sample size/power considerations for comparing symptom burden between ACU vs. OPI at Day 7, we calculated the smallest standardized effect size (aka, Cohen's d) we will be able to detect with 80% power, given our sample sizes of 150 in each of the two arms. To estimate this smallest detectable effect size, we used the methods of Lu, Luo, & Chen (2008), which describes sample size calculations for a class of analyses called the “mixed model for repeated measures” (MMRM) in randomized clinical trials with participant attrition. Our LMM analyses fall under this MMRM class of analyses. Using the “power.mmmr”

function from the R package “longpower”, we applied the formulas in Lu et al. (2008) to our study design and assumptions to derive the smallest detectable effect size for the coefficient of the time-by-arm interaction term in our LMM (with time including only the Day 0 and Day 7 assessments, see Section 14.2), which we transformed to represent the standardized mean difference (aka, Cohen’s  $d$ ) of the changes in symptom burden from baseline between the two arms at Day 7 post-HSCT. With 150 participants in each of the two arms, we will have power of 0.80 to detect an effect size for symptom burden as small as 0.41 (standardized difference, Cohen’s  $d$ ) at Day 7 between acupuncture vs. usual care, assuming 10% attrition, correlation between baseline and Day 7 symptom burden scores of 0.50, and two-sided alpha of 0.01. The MDASI-BMT Total Symptom Severity score does not have an empirically-established minimum clinically important difference (MCID). A research-based rule-of-thumb for PRO instruments lacking empirical MCIDs is to adopt a standardized difference of 0.50 as the MCID. Given our detectable effect size of 0.41, we will be able to detect a MCID in symptom burden between the two arms.

For Aim 2, we will test whether mean ACU pain scores are non-inferior to mean OPI pain scores at two timepoints, Day 7 and Day 90. To limit the type I error rate for this family of two tests to 0.05, we will use a significance threshold for each test of 0.025. The Aim 2 key endpoint is Day 7 pain scores, since pain due to HiChemo is expected to peak around Day 7 and resolve well before Day 90 for both study arms. We present power considerations below for the Day 7 non-inferiority test. The same assumptions apply to the Day 90 test; however, we expect ACU pain scores to be well within our non-inferiority margin by Day 90. We will have 80% power to find mean ACU pain scores non-inferior to mean OPI pain scores within a non-inferiority margin of 0.34 standard deviations (SD), assuming 300 patients, 10% attrition, and one-sided significance threshold of 0.025. Our non-inferiority margin (0.34 SD) is smaller than the typical minimum clinically important difference (MCID) for self-report measures (i.e., MCID = 0.50 SD for BPI). Therefore, this margin represents an acceptable pain control benchmark for ACU in comparison to OPI.

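### The fixed 0.02/0.02/0.01 alpha split is valid, but weighted Holm with the same starting levels gives each primary endpoint more power at the same overall 0.05

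*Combined protocol and SAP*

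**What the plan says.** Section 14.1 treats Day 7 opioid use, Day 90 opioid use and Day 7 symptom burden as one family with an overall error rate of 0.05. It then fixes the levels for the two opioid endpoints: "we will allocate alpha = 0.02 to each of the tests of opioid use at Day 7 and at Day 90". The third endpoint receives what is left of the 0.05: "we will allocate alpha = 0.01 to the test of symptom burden at Day 7".

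All power statements use those levels. For 10% versus 25% users with 135 evaluable patients per arm and p<0.02, the plan states that "we will have 81% statistical power to detect this Day 90 difference between the two arms". It describes the underlying test as "using logistic regression analysis and a two-sided significance test". Power is put at 96% if the OPI rate is 30%. Day 7 opioid power is not quantified. It is called similar to Day 90, with this remark: "we most likely have higher power at Day 7 due to lower attrition and potentially a larger effect size at Day 7".

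For symptom burden, the smallest effect that "we will be able to detect with 80% power, given our sample sizes of 150 in each of the two arms" is given as d = 0.41 at two-sided 0.01. The plan states no expected effect, only a benchmark: "A research-based rule-of-thumb for PRO instruments lacking empirical MCIDs is to adopt a standardized difference of 0.50 as the MCID".

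Section 14.2.2 tests Hypotheses 1a, 1b and 1c in separate models. Neither section has a step-down, gatekeeping or alpha-recycling rule for these endpoints, so the plan is a weighted Bonferroni split.

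**The concern.** Under a fixed split, the alpha spent on an endpoint that succeeds is not used again. Suppose Day 7 opioid use and symptom burden are both significant and Day 90 opioid use gives p = 0.03. The plan must call Day 90 negative. Weighted Holm would call it positive at the same family-wise error rate. Section 14.1 sizes the trial on Day 90 opioid use alone and accepts roughly a one-in-five chance of missing the assumed effect, so this is the endpoint where the unused alpha matters most.

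**Working it through.** **Inputs.** From 14.1: levels 0.02, 0.02 and 0.01; Day 90 power 81% (10% vs 25%) or 96% (10% vs 30%); symptom burden 80% at d = 0.41, with benchmark d = 0.50. Assumed: Day 7 opioid power (81% or 96%), and the correlation between test statistics, which the documents do not give (taken as 0 to 0.7, and 0.9 as an extreme).

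**The plan's own figures.**
- Alpha: 0.02 + 0.02 + 0.01 = 0.05.
- Day 90, pooled two-proportion formula: null SE = √(2 × 0.175 × 0.825/135) = 0.0462; alternative SE = √((0.09 + 0.1875)/135) = 0.0453; z = (0.15 − 2.326 × 0.0462)/0.0453 ≈ 0.94, so power is 82.5%. Other standard formulas give 78.0% to 83.7%. The stated 81% is reproduced.
- Symptom burden: SE = √(2 × (0.75/135 + 0.25/150)) = 0.120; detectable d = (2.576 + 0.842) × 0.120 = 0.41, as stated.

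**Weighted Holm levels** (weights 0.4/0.4/0.2):
- An opioid endpoint starts at 0.02. It moves to 0.05 × 0.4/0.8 = 0.025 if only symptom burden has been rejected, to 0.05 × 0.4/0.6 = 0.033 if only the other opioid endpoint has been rejected, and to 0.05 if both have.
- Symptom burden starts at 0.01. It moves to 0.05 × 0.2/0.6 = 0.0167 after one opioid rejection and to 0.05 after both.

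No level ever falls below its starting value, so nothing that the fixed split rejects can be lost. The first step is identical, so the chance of at least one success is identical too.

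**Check by hand at correlation 0 (81/81/80%).** An 81% test at 0.02 has mean 2.326 + 0.878 = 3.204. Its power is 83.2% at 0.025, 85.9% at 0.033 and 89.3% at 0.05. The extra Day 90 rejections are:
- p from 0.02 to 0.025 (2.22 points of probability) needs either other endpoint: 1 − 0.19 × 0.20 = 0.962, giving 2.14.
- p from 0.025 to 0.033 (2.69 points) needs Day 7 opioid use: 0.81 + 0.022 × 0.80 = 0.828, giving 2.23.
- p from 0.033 to 0.05 (3.42 points) needs both: 0.81 × 0.847 + 0.022 × 0.80 = 0.704, giving 2.41.

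The total is 6.8 points.

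**Simulation, 1,000,000 draws per cell, 81/81/80%, all effects real:**

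| Correlation | Each opioid endpoint | Symptom burden | All three, fixed → Holm | At least one, both rules |
|---|---|---|---|---|
| 0 | 87.8% (+6.7) | 90.5% (+10.4) | 52.6 → 73.3% | 99.3% |
| 0.3 | 87.0% (+6.0) | 89.2% (+9.2) | 58.1 → 75.7% | 97.4% |
| 0.5 | 86.5% (+5.5) | 88.3% (+8.3) | 62.2 → 77.8% | 95.3% |
| 0.7 | 85.9% (+4.9) | 87.3% (+7.3) | 66.8 → 80.2% | 92.4% |
| 0.9 | 84.8% (+3.8) | 85.6% (+5.6) | 72.9 → 82.9% | 87.7% |

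**Other scenarios, gains in points, correlation 0 to 0.7, all effects real.** For d = 0.50 the mean is 3.417 × 0.50/0.41 = 4.17, which is about 94% power at 0.01.

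| Scenario | Opioid | Symptom |
|---|---|---|
| Opioid 81/81%, d = 0.50 | 5.7–7.2 | 1.3–3.5 |
| Opioid 96/96%, d = 0.41 | 1.3–2.1 | 11.7–12.3 |
| Opioid 96/96%, d = 0.50 | 1.6–2.2 | 3.2–4.1 |
| Day 7 96%, Day 90 81%, d = 0.41 | Day 7 0.6–1.9; Day 90 6.6–7.6 | 9.3–11.4 |

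**When other effects are null (81/81/80% otherwise, correlation 0 to 0.7).** Day 90 gains about 3 to 4 points if symptom burden is null, 1.4 to 1.9 if Day 7 opioid use is null, and about 0.1 if both are null.

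**Cost in false positives.** With the other two effects real, the rejection rate for a null Day 90 effect goes from 2.0% to 3.7–4.4%, and for null symptom burden from 1.0% to 3.3–4.1%. The largest simulated family-wise error was 0.0491.

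**The case against.** The plan has no defect to repair. A prespecified weighted Bonferroni split is standard, meets the stated 0.05 exactly, and delivers the Day 90 power the plan set out to have. That stands, and it is why this is an advisable improvement and not a correction.

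The 5-to-7-point figure belongs to the plan's conservative case. Section 14.1 says that a larger effect than in the pilot is expected. At 96% opioid power the gain is only 1.3 to 2.2 points per opioid endpoint, and if Day 7 is the stronger endpoint it gains little itself. That also stands. In the same situation, though, Day 90 gains most (6.6 to 7.6 points if it stays at 81%).

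A self-contained 2% level for Day 90 can be defended. Acupuncture ends by Day 15 (section 10.0), and section 3.0 expects no residual transplant-related pain by Day 90, so real Day 7 effects with no Day 90 effect are plausible. Holm then about doubles the Day 90 false-positive rate, although it stays within the 0.05 the plan accepts.

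Fixed levels also give simple matching intervals, and each Day 7 conclusion stands alone. Under Holm, a Day 7 result just above its first-step level may have to wait for the Day 90 test. The plan gives neither reason for its choice.

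Finally, the comparator is usual care without sham, so treatment is not masked by a sham procedure, and relaxing thresholds by amendment may affect credibility. The documents do not show how far the trial has progressed, so whether the amendment can still be made in time is unknown.

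**Conclusion.** The concern holds as a missed efficiency. The fixed split is valid but never more powerful than weighted Holm with the same weights, and it is less powerful for each primary endpoint whenever another one succeeds. If all three effects are real, the gain per opioid endpoint is about 5 to 7 points at 81/81/80% power with correlations up to 0.7, nearer 4 at 0.9, and about 1 to 2 at 96% opioid power. The symptom-burden gain runs from about 1 to 12 points across the scenarios for correlations up to 0.7. The gain needs at least one other endpoint to succeed. The results rest on normal test statistics, an assumed correlation and an assumed Day 7 opioid power. That Holm never does worse rests on none of these.

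**What to change.** Before any between-arm primary outcome data are examined, amend 14.1 to read, for example:

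> *The three primary hypotheses will be tested by the weighted Holm procedure at overall two-sided alpha 0.05 with initial weights 0.4 (Day 7 opioid use), 0.4 (Day 90 opioid use) and 0.2 (Day 7 symptom burden). Alpha from a rejected hypothesis is redistributed in proportion to the remaining weights.*

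Repeat the rule in 14.2.2, where Hypotheses 1a to 1c are tested. In 14.1, label p<0.02 with 81% and 96%, and alpha 0.01 with d = 0.41, as first-step figures; they remain as minimum power.

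Report Holm-adjusted p-values, with 95% intervals labelled as unadjusted. Do not use fixed 98%/98%/99% intervals as the decision criterion, because they include no effect for every rejection that the step-down adds. For example, 19 versus 34 users of 135 per arm gives OR = (19 × 101)/(34 × 116) = 0.49, p = 0.023, a 98% interval of 0.23 to 1.02 and a 95% interval of 0.26 to 0.91. Holm rejects if either other endpoint has been rejected. A 95% interval that excludes no effect is necessary for Holm success but does not establish it.

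The change needs no added patients, visits or data. Because it alters the primary decision rule, it needs a dated amendment, and the record should show that it preceded any look at between-arm results. If the team prefers the fixed 2% level for Day 90, it should keep the split and state that reason in 14.1.
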